## **5. STUDY POPULATION**

### **5.1. General**

The ITT analysis set (see Section 3.1) will be used for all study population summaries unless otherwise specified. Summaries will be presented by treatment group and all patients.

### **5.2. Patient Disposition**

Data from patients screened; patients screened but not randomized and reason not randomized; patients randomized (ITT); patients randomized but not treated; patients in the safety and other analysis sets; patients who completed the double-blind treatment; patients who enter open-label treatment period; patients who did not complete double-blind treatment will be summarized using descriptive statistics. Data from patients who did not complete double-blind treatment will also be summarized by reason using descriptive statistics.

This summary will include all patients.

Patients who completed study or patients withdrew from the study by reason will be summarized once the study is completed.

### **5.3. Demographics and Baseline Characteristics**

The demographic data will be collected at the screening visit after the patient signs the informed consent form. Patient demographic data including age, age group (<65 or ≥65 years old), gender, race, race group (white or other), ethnicity, baseline weight (kg), baseline height (cm), and baseline body mass index (kg/m^2) will be summarized using descriptive statistics for all analysis sets.

Baseline characteristics including time since the head trauma, duration of PTH history (less than 12 month since the brain injury versus greater or equal to 12 month since the brain injury), diagnosis of PTH, preventive medication use (yes or no) at screening or baseline, use of any acute headache medication (opioid, barbiturate, triptan, and NSAIDS) during the baseline period (yes or no), use of prescription abortive headache medication (opioid, barbiturate, and triptan) during the baseline period (yes or no), and monthly average number of headache days of at least moderate severity during the baseline period will be summarized for the ITT analysis set using descriptive statistics. No inferential analyses will be performed.

The time (in year) since the head trauma will be calculated as (the date of informed consent – the date of head trauma + 1)/365.25. Rules for handling partial head trauma date are in Section 4.3.

### **5.4. Medical History**

All medical history abnormalities will be coded using the Medical Dictionary for Regulatory Activities (MedDRA). The incidence of medical history abnormalities will be summarized using descriptive statistics by system organ class (SOC) and preferred term. Patients are counted only once in each SOC and only once in each preferred term.

### **5.5. Prior Therapy and Medication**

All prior medications or therapy will be coded using the World Health Organization Drug Dictionary of medical codes (WHO Drug). The incidence of prior medications or therapy will be summarized by therapeutic class and preferred term using descriptive statistics. Patients are counted only once in each therapeutic class category, and only once in each preferred term category. Prior medications will include all medications taken within 3 months prior to the administration of the first dose of the IMP.

The prior medications will be summarized by the following indications categories:

- butalbital for post traumatic headache
- butalbital for other reason than post traumatic headache
- ergots for post traumatic headache
- ergots for other reason than post traumatic headache
- NSAIDS for post traumatic headache
- NSAIDS for other reason than post traumatic headache
- opioids for post traumatic headache
- opioids for other reason than post traumatic headache
- preventive medication from the study protocol for post traumatic headache
- preventive medication from the study protocol for other reason than post traumatic headache
- triptans for post traumatic headache
- triptans for other reason than post traumatic headache
- other

### **5.6. Childbearing Potential and Methods of Contraception**

Information related to reproductive system findings will be collected at the screening visit. Data will be listed.

### **5.7. Physical Examinations**

Patients with at least 1 abnormal finding (overall) and abnormal findings for each category will be summarized.

### **5.8. Study Protocol Deviations**

Data from patients with any important protocol deviations during the study will be summarized overall and for each category using descriptive statistics.

## 6. EFFICACY ANALYSIS

### 6.1. General

The FAS will be used for all efficacy analyses unless otherwise noted. Analyses of the primary and secondary endpoints will be repeated for the PP analysis set.

Analyses for endpoints related to double-blind treatment (up to visit 5/12-week) will be performed after DB lock for double-blind treatment. The analyses will be by treatment groups.

Analyses for endpoints related to open-label treatment (from visit 5/12-week to the end of the study) will be performed after study completion.

For data not collected daily, baseline is the last observed data before the administration of the first dose of the IMP. For data collected daily in the e-diary, baseline will be derived from the baseline period (from the day of the informed consent to before the administration of the first dose of the IMP). Details are provided in Section 6.1.3.

For patients who do not have Visit5/Week 12 assessment and do not continue in the open-label period but have assessment at EOS, the assessment at EOS will be used as Visit 5/Week 12.

Derived efficacy variables are

- monthly average number of headache days of at least moderate severity
- monthly average number of headache days of any severity
- monthly average number of neck pain days of any severity
- monthly average number of days of use of any acute headache medication
- monthly average number of days of use of opioid analgesics for headache
- average severity of headache
- average daily peak headache severity

Summaries will be presented by treatment group as randomized unless otherwise noted. In addition to inferential statistics, descriptive statistics will be presented in by-visit or by-analysis-window summaries. A missing category will be presented if applicable. Derived endpoints will be listed.

#### 6.1.1. Posttraumatic Headache Data from E-diary

Information about PTH will be recorded in the e-diary daily. Corresponding PTH questions are in [Appendix A](#) (questions A1, B1 through B3, and C1 through C9). Patients will record headache(s) occurred during last 24 hours. The recording window on e-diary device is “Yesterday morning 6:00 am to today at 5:59 am”. Patients can record missed entry for “the day before yesterday morning 6:00 am to yesterday at 5:59 am”, maximum 48 hours recall window is allowed.

Date of a headache is derived as the following

- headache report date -1 day if the recording is for 24 hours recall
- headache report date – 2 days if the recording is for 48 hours recall

Baseline and postbaseline monthly average number of headache days for a patient within an analysis window will be calculated based on data available and prorated to 28 days using formula A.

**6.1.2. Data Derivation**

The **monthly average** of an efficacy variable will be calculated and prorated to 28 days as follows:

$$\frac{\sum \text{efficacy endpoint data during the period}}{\text{Number of Days with assessments recorded in the eDiary during the period}} \times 28 \text{ [A]}$$

The “efficacy endpoint data” will be “number of headache days of at least moderate severity”, “number of headache days of any severity”, “number of neck pain days of any severity”, “number of days of use of any acute headache medication”, and “number of days associated with use of opioid analgesics for headache” observed during a treatment period.

The “period” will be the baseline period for baseline calculation or 12-week double-blind treatment period or monthly analysis window [eg. Month 1 (weeks 1 to 4), Month 2 (weeks 5 to 8), Month 3 (weeks 9 to 12)] for post-baseline calculations.

The **percentage of reduction** from baseline in the monthly average number of headache days will be calculated as follows:

$$\frac{\text{baseline value} - \text{postbaseline value}}{\text{baseline value}} \times 100\% \text{ [B]}$$

where baseline value and postbaseline value are the monthly average calculated using formula A.

**6.1.3. Analysis Windows for E-diary Data**

**Baseline** window is the period from the day of the informed consent to before the administration of the first dose of the IMP. The baseline monthly average value for an efficacy variable will be calculated based on data recorded in the baseline window and prorated to 28 days using formula A.

**Postbaseline 4-week (monthly) analysis windows** will be determined based on the actual dosing date as follows:

- Month 1 (weeks 1 to 4): from the day of the first dose of the IMP administration to the day before the IMP administration at visit 3 (week 4/dose 2) or to the end of e-diary in the double-blind treatment period if a patient only receives dose 1;
- Month 2 (weeks 5 to 8): from the day of the IMP administration at visit 3 (week 4/dose 2) to the day before the IMP administration at visit 4 (week 8/dose 3) or to the end of e-diary in the double-blind treatment period if a patient only receives dose 1 and dose 2;

- Month 3 (weeks 9 to 12): from the day of the IMP administration at visit 4 (week 8/ dose 3) to the end of e-diary of the double-blind treatment period.

Notes:

1. The end of e-diary of the double-blind treatment period is defined as the date of last IMP administration + 27 days.
2. There will be no double-blind IMP administration at visit 5;
3. A 4-week analysis window may contain <28, 28, or >28 days.

The monthly average of an efficacy variable for each analysis window will be calculated based on data recorded in the e-diary and prorated to 28 days using formula A. Missing data handling methods are provided in Section 6.1.4.

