## 4.3. Withdrawal Criteria and Procedures for the Patient

Each patient is free to withdraw from the study or discontinue from IMP at any time, without prejudice to their continued care. Patients must be withdrawn from the study if any of the following events occur:

- 1. Patient withdraws consent or requests discontinuation from the study for any reason.
- 2. Patient develops an illness that would interfere with his/her continued participation.
- 3. Patient is noncompliant with the study procedures and assessments or administration of IMPs in the opinion of the investigator.
- 4. Patient takes prohibited concomitant medications as defined in this protocol.
- 5. A female patient has a confirmation of pregnancy during the study from a positive pregnancy test.
- 6. The sponsor requests withdrawal of the patient.
- 7. Patient experiences an adverse event or other medical condition, which indicates to the investigator that continued participation is not in the best interest of the patient.
- 8. Patient scores a 5 on the C-SSRS assessment.

Due to over-enrollment, meaning that the total number of patients that may be recruited for the study or when the site enrollment limit has been reached, the sponsor may decide to cancel patient participation in the study, either because they volunteered to withdraw or because they are one of the last patients to have been screened. Therefore, they will not be permitted to be randomized. The patient will be reimbursed for reasonable transportation, parking and meal costs, if necessary. In case of cancellation, the patient should discuss with their physician options for appropriate treatment.

Patients should be treated with standard of care after withdrawal from or termination of the study as appropriate.

Investigators should attempt to obtain information on patients in the case of withdrawal from the study or discontinuation from IMP. Results of any evaluations and observations, together with a narrative describing the reason(s) for withdrawal from the study or discontinuation from IMP, must be recorded in the source documents. The case report form (CRF) must document the primary reason for withdrawal from the study or discontinuation from the IMP.

See Appendix E for information regarding how the study will define and address lost to follow-up patients to help limit the amount and impact of missing data.

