A sample size of 154 patients (77 evaluable patients per treatment group) willwas calculated to provide 80% power to detect a treatment difference of 2.0 days in the monthly average (assuming a common SD of 4.4 days) at a 2-sided alpha level of 0.05. Assuming a 10% discontinuation rate, 172 patients (86 patients per treatment group) willwere planned to be randomized in the study.  Study recruitment was discontinued at 87 patients due to challenges to enrollment and not for any safety concerns.	A sample size of 154 patients (77 evaluable patients per treatment group) was calculated to provide 80% power to detect a treatment difference of 2.0 days in the monthly average (assuming a common SD of 4.4 days) at a 2-sided alpha level of 0.05. Assuming a 10% discontinuation rate, 172 patients (86 patients per treatment group) were planned to be randomized in the study.  Study recruitment was discontinued at 87 patients due to challenges to enrollment and not for any safety concerns.	Clarification to the sample size as study enrollment was discontinued due to challenges to recruitment prior to reaching the target sample size.
Section 9.2.4 Per-Protocol Analysis Set		I
The per-protocol (PP) analysis set is a subset of the ITT analysis set including only patients without any major protocol deviations or unexpected drug concentration findings. Major protocol deviations will be determined before unblinding and database lock.	The per-protocol (PP) analysis set is a subset of the ITT analysis set including only patients without any major protocol deviations. Major protocol deviations will be determined before unblinding and database lock.	The definition of the per-protocol analysis set was modified as this is a subset of patients who completed the study as intended, only with a lack of major protocol deviations.
In the PP analysis set, treatment will be assigned based on the treatment patients actually received, regardless of the treatment to which they were randomized.		

Original text with changes shown	New wording	Reason/Justification for change

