## 6.2. Primary Efficacy Endpoint and Analysis

### 6.2.1. Definition

The primary efficacy endpoint is the mean change from baseline (baseline period) in the monthly average number of headache days of at least moderate severity during the 12-week period after the first dose of the IMP.

The primary efficacy endpoint for this study will be derived from PTH data (presence of headache [yes/no] and peak severity [mild/moderate/severe]) collected daily using an electronic headache diary application.

Headache days of at least moderate severity will be derived from the e-diary data as described in Section 6.1.1. The 12-week period is the period from administration of the first dose of IMP to the EODBT as defined in Section 4.4. The monthly average number of headache days of at least moderate severity will be calculated using formula A. Missing data handling method is provided in Section 6.1.4.

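### SAP 6.1.3 closes the double-blind diary 27 days after the last dose, but 6.2.1 and 6.3.1 run the 12-week period to visit 5 or early termination, so entries made after dosing stops have no consistent place in the analysis

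*SAP*

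**What the plan says.** **Monthly windows.** SAP 6.1.3 starts each 4-week window at a dose and ends it the day before the next dose. If there is no later dose, the window runs to the end of the double-blind diary, and "The end of e-diary of the double-blind treatment period is defined as the date of last IMP administration + 27 days". The same section notes that "A 4-week analysis window may contain <28, 28, or >28 days".

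**12-week period.** SAP 6.2.1, for the primary endpoint, says "The 12-week period is the period from administration of the first dose of IMP to the EODBT as defined in Section 4.4". SAP 6.3.1 uses the same end for the 12-week responder endpoint. SAP 4.4 defines EODBT as visit 5/Week 12, or the early termination visit for patients who neither complete the double-blind period nor enter the open-label period.

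**Missing diary data (SAP 6.1.4).** With at least 10 diary days in a window, the patient's own data are prorated to 28 days. With fewer than 10, the window takes the mean of the same arm. Active-arm patients who do not complete the double-blind period because of lack of efficacy, death or an adverse event have the remaining days filled from the placebo average. That formula uses N = 28 or N = 84 and requires at least one diary day in the window.

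**Stopping treatment.** Protocol 4.3 treats stopping the injections and leaving the study as separate events: "Each patient is free to withdraw from the study or discontinue from IMP at any time". Protocol 6.1 asks for a diary entry on every day of the baseline and double-blind periods.

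**The concern.** A patient can stop injections, stay in the study and go on recording. Two stated rules then disagree about which of that patient's entries count. Under 6.1.3, months without a dose have no window, so the entries exist but are not used, and 6.1.4 treats those months as missing. Under 6.2.1 the same entries are part of the 12-week period.

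Two things follow. The primary value for such a patient depends on which section the programmer follows. And the MMRM, which SAP 6.2.3 presents as the check on missing data, is run on monthly values in which observed outcomes have been replaced by a group mean. The monthly change endpoints in 6.3.3 are built the same way. The monthly responder endpoints in 6.3.2 may be too: the heading of the rule in 6.1.4 limits it to ANCOVA and MMRM, but its closing note extends it to all headache-day endpoints.

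The dose-anchored rule also leaves a gap. If dose 2 is missed and dose 3 is given, 6.1.3 defines no boundary between Month 1 and Month 2, because its fallback covers only patients who never receive a later dose.

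**Working it through.** **Inputs.** Visits at Day 28±3, 56±3 and 84±3, with the first dose on Day 0 (Protocol Table 1). SAP 4.4 numbers the first-dose day as study day 1. The diary cut-off is last dose + 27 days (SAP 6.1.3); N is 28 or 84 (SAP 6.1.4). The design difference is 2.0 days with SD 4.4 (Protocol 16.1, new wording for section 9.1). Recruitment stopped at 87 patients (Protocol 3.2).

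**1. The plan's own figures.** Dose day to dose day + 27 is 28 days, and three on-schedule windows give 84, matching N. The sample size also reproduces: 2 × (1.96 + 0.84)² × 4.4² / 2.0² gives 76 per arm by the normal approximation, and the t-test gives 76.95, so 77; 77/0.9 = 85.6, so 86. It serves here only to give 2.0 days as a scale.

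**2. Where the cut-off falls for a patient who records to study day 84.**

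| Doses received | Last study day kept under 6.1.3 | Days in no monthly window |
|---|---|---|
| 1 | 1 + 27 = 28 | 84 - 28 = 56 (67%) |
| 2 | 29 + 27 = 56 | 84 - 56 = 28 (33%) |
| 3 | 57 + 27 = 84 | 0 |

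**3. Completers.** Visit 5 minus (dose 3 + 27), in protocol days: nominal 84 - (56 + 27) = +1; smallest 81 - (59 + 27) = -5; largest 87 - (53 + 27) = +7. Formula A divides by days recorded, so this hardly moves a completer's value.

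**4. What each analysis does with the later entries of a one-dose patient who records to visit 5.**

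- Primary ANCOVA, following 6.2.1: all entries are used.
- Primary ANCOVA, following the +27 cut-off: up to 28 early days remain. With at least 10 recorded, the patient's own early data are prorated, and no arm mean is used.
- MMRM and monthly change endpoints: Months 2 and 3 have no diary days, so each takes the same-arm mean. If the patient falls under the active-arm placebo rule, that formula does not cover a window with no diary days.

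**5. Illustration (assumed values).** Month 1 has 10 headache days, Months 2 and 3 have 16 each, and the arm mean is 11.

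- All entries: (10 + 16 + 16)/3 = 14.0
- +27 cut-off, prorated: 10.0
- Monthly route with arm means: (10 + 11 + 11)/3 = 10.7

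With 87 patients at 1:1, an arm has about 43.5. One such patient moves the unadjusted arm mean by (14.0 - 10.0)/43.5 = 0.09 days.

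**6. Size across a range (assumption, not in the documents).** Suppose a fraction p of the active arm stops, keeps recording and loses the whole 2.0-day effect once the window closes, with no counterpart in the placebo arm. The overstatement of the 12-week difference is p × f × 2.0, where f is the share of the period dropped.

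| p | f = 1/3 (two doses) | f = 2/3 (one dose) |
|---|---|---|
| 2% | 0.01 | 0.03 |
| 5% | 0.03 | 0.07 |
| 10% | 0.07 | 0.13 |

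The largest entry is 6.7% of 2.0 days. In one month that is wholly replaced by an arm mean still showing the full effect, f = 1, and p = 2% to 10% gives 0.04 to 0.20 days.

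**7. Fixed N.** Month 2 can last from 53 - 31 = 22 to 59 - 25 = 34 days, while 6.1.4 keeps N at 28.

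**The case against.** The strongest reply is that the affected patient is rare. Many routes off treatment also lead out of the study: noncompliance, prohibited medication and pregnancy (Protocol 4.3), unblinding (5.9.2) and the liver stopping rules (Appendix I). Patients who withdraw have visit 8 procedures at their final visit, and Table 1 has no off-treatment schedule. The endpoints that lose data are not in the testing sequence of SAP 7, which holds only the primary, a 12-week responder endpoint and HIT-6. All of this stands, and it limits the size of the problem. It does not remove the conflict between 6.1.3 and 6.2.1, nor the loss of entries from anyone who does stay.

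Four stronger readings are tempting, and the documents do not support them.

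- **Arm means replace these data in the primary analysis.** They do not. Under 6.2.1 the entries are kept; under the +27 cut-off the patient's own data are prorated once 10 days are recorded.
- **The replacement flatters fremanezumab.** Active-arm patients who fail to complete because of lack of efficacy, death or an adverse event are meant to receive placebo values. For the others, no direction is given.
- **This breaks analysis as randomized.** That statement in SAP 3.4 concerns the arm to which a patient is assigned, not which diary days are used.
- **The placebo formula will subtract days because N - X can reach 28 - 34 = -6.** This needs a fully recorded 34-day Month 2 and the formula applied to a window already finished. The window holding the last dose is always 28 days, and SAP 1.6 limits the filling to the remainder of a window.

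**Conclusion.** The point holds as an inconsistency in how the periods are defined, with an avoidable loss of recorded data. The end of the 12-week period is stated in two ways. The gap is trivial for completers but about 56 or 28 days for a patient who stops after dose 1 or dose 2 and records to visit 5. Those days are lost to the MMRM and the monthly change endpoints, and possibly to the monthly responder endpoints. For the primary endpoint they are kept or lost according to the section followed. The missed-dose-2 boundary is undefined, and N does not follow the actual window length.

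The effect on the trial's conclusion is likely small: 0.03 to 0.13 days on the 12-week difference for 5-10% stopping, under an assumption chosen to be unfavourable. The documents give neither the number of such patients nor the direction of bias. With 87 patients rather than the planned 172, one patient still carries some weight, which is reason enough to settle the derivation before unblinding.

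**What to change.** Before the double-blind database lock, amend the SAP as follows.

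- Use one end of period in 6.1.3, 6.2.1 and 6.3.1: the earliest of study day 84, the day before the visit 5 dose, and the early termination date.
- Define monthly windows by study day from first dose (1-28, 29-56, 57 to end of period), whatever doses follow. This also closes the missed-dose-2 gap.
- Use every diary entry recorded in those windows, whether or not injections continued, and impute only days with no entry.
- In 6.1.4, set N to the planned length of the window and floor N - X at 0. N is 28 or 84 unless visit 5 comes early. With visit 5 on protocol Day 81 (study day 82), Month 3 covers study days 57-81, so N is 25 for that month and 81 for the period.
- State whether the imputation applies to the monthly responder endpoints.

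The cost is SAP wording and programming, with no new data collection. The downside is that windows may no longer line up with injection dates, by a few days.
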